## 4.2 Minimization of Bias

Potential sources of bias in this study may result from selection of participants, treatment of participants, and evaluation of study data. The following methods have been incorporated into the study protocol to minimize potential bias:

- Participants will be screened to confirm eligibility for enrollment with defined inclusion/exclusion criteria prior to Mock-RP swallowing attempt.
- All Site and Sponsor personnel will be trained on their respective aspects of the study using standardized training materials.
- All study personnel will be trained on and required to follow the CIP.
- All study investigators will be required to provide Financial Disclosure.
- Rani Therapeutics will monitor the investigation for adherence to GCP the CIP and accurate data reporting.

## 5 STUDY SAMPLE SIZE

As a prospective, single-center, open-label, single-arm, observational study, no statistical criteria for sample size are required. A total of 30 to 50 participants in each age group (21-50, 51-65, 66-75), for a total of up to 150 participants will provide sufficient data to characterize the endpoints, as well to evaluate swallowing trends between subgroups.

## 6 STUDY SITE INFORMATION

### 6.1 Agreements

Rani Therapeutics will sign a Clinical Trial Agreement (CTA) between Rani Therapeutics and the principal investigator (PI) and/or investigative site. This agreement will outline the financial and contractual arrangements between the parties.

### 6.2 Institutional Review Board (IRB)

IRB approval of the current CIP, Informed Consent Form (ICF), and any other study materials provided to prospective participants is required prior to enrolling any participants. Recruitment materials must be approved by the IRB before their presentation to prospective participants. Continuing review is required throughout the duration of the study until the time of study closure.

### 6.3 Investigator Responsibilities

Before participating in the study, all Investigators must agree to respect and fulfill the terms of this Investigational Plan.

- The investigator is responsible for ensuring this study is conducted according to the signed agreements, this CIP, all applicable regulations, and any conditions imposed by the IRB.

- The investigator is responsible for obtaining the written and dated approval/favorable opinion of the IRB for the clinical investigation before obtaining informed consent or allowing any participant to participate.
- The investigator is responsible for ensuring all IRB policies and procedures are followed.
- The investigator is responsible for protecting the rights, safety, and welfare of participants under the investigator's control.
- The investigator is responsible for obtaining informed consent.
- The investigator must document and explain any deviation from this CIP.
- The investigator is responsible for control of study CTM in his or her facility and must ensure they are only used by authorized persons for participants in this study and must ensure they are returned to Rani Therapeutics when requested.
- An investigator must disclose sufficient conflicts of interest, including financial information. The investigator must promptly update the information if any relevant changes occur throughout the study and for one year following study closure.
- The investigator must maintain a list of appropriately qualified persons to whom the investigator has delegated study activities. This document is referred to as the Delegation of Authority Log for this study. Even though tasks may be delegated, the investigator is ultimately responsible for the conduct of the study at his or her institution. The investigator must not allow persons on the delegation log to perform study activities until they are trained by the Rani Therapeutics study team.
- The investigator must have sufficient time and resources to properly conduct and complete the study.
- The investigator must maintain accurate and complete records relating to the investigation.
- The investigator must be responsible for all study related medical decisions and ensure that adequate medical care is provided to a participant for adverse events.

The investigator should ensure the accuracy, completeness, and timeliness of all data and reports submitted to Rani Therapeutics and the IRB.

#### **6.4 Sponsor Responsibilities**

The Sponsor responsibilities include, but are not limited to:

- Selecting appropriately qualified principal investigators.
- Providing investigators with the information they need to conduct the investigation properly.
- Ensuring proper monitoring of the investigation.

	PILL SWALLOW STUDY PROTOCOL	Doc No.:	CP-0003
		Revision:	C
		Page:	Page 13 of 14

- Securing compliance and maintain records to document the compliance of all parties involved in the clinical investigation.

Rani Therapeutics and industry personnel can provide technical support to the Investigator and other health care personnel (collectively HCP) as needed during testing required by the protocol and follow-ups. Support may include HCP training, addressing HCP questions, or providing clarifications to HCPs concerning the procedures and forms related to the protocol.

In addition, Rani Therapeutics may perform certain activities to ensure study quality. These activities may include:

- Observing testing to provide information relevant to protocol compliance.
- Reviewing collected data and study documentation for completeness and accuracy.

Rani Therapeutics will not:

- Practice medicine.
- Provide medical diagnosis or treatment to participants.
- Discuss a participant's condition or treatment with a participant without the approval and presence of the HCP.
- Independently collect critical study data.
- Enter data in electronic data capture systems.

## 6.5 Study Training

Persons who conduct study activities under this CIP must be trained prior to performing study activities. The site PI must be trained before the site may be activated. PIs will be trained on the following:

- CIP, including but not limited to visit procedures, informed consent, investigator responsibilities, investigational CTM usage and handling, data collection, electronic data capture system, adverse events, reporting requirements, participant withdrawal, and study deviations.
- ICH Guideline on Good Clinical Practices (GCP) E6, Section 4, Investigator
- Investigator responsibilities described in 21 CFR 312 Subpart D

All other site and sponsor personnel who perform study activities must be trained on study activities relevant to their roles and responsibilities.

## 6.6 Site Selection

Sites will be selected based on research infrastructure, the availability of the potential participant pool that meets study inclusion criteria, and the site's ability to perform the research in compliance with the CIP.

## 6.7 Site Activation

Site activation is defined as the point in time where the sponsor notifies the PI in writing that the study may begin, and participants may be consented (enrolled) at his or her site. All local regulatory requirements must be fulfilled before the site can be activated. Rani Therapeutics will provide each PI written notification upon site activation. The following must be complete and received by Rani Therapeutics prior to a site's activation:

- Financial Disclosure Form: The PI must disclose any financial arrangements he or she has with Rani Therapeutics that meet the following requirements per 21CFR54:
  - Payment to the PI that could be influenced by the outcome of the trial
  - Any other significant payments ( $\geq \$25,000$ ), such as research grants, consulting, etc.
  - Any proprietary interest in the investigational CTM
  - Any significant equity interest in Rani Therapeutics ( $\geq \$25,000$ )
- Confirmation that PI has completed study training
- IRB approval of the CIP
- IRB approved ICF
- Current Curriculum Vitae (CV) of the PI
- Fully executed CTA between Rani Therapeutics and the PI and/or Institution

Other study site personnel, including sub-investigators, may not participate in study activities until compliance with all individual requirements are documented.

The following must be completed before individual site personnel may perform study activities:

- Site activation must be complete (the PI must have all aforementioned items completed)
- Training pertinent to the individual's role
- Individuals must be named on the list of appropriately qualified persons to whom the investigator has delegated significant study-related duties
- Current CV (for sub-investigators only)
- Financial Disclosure Form (for sub-investigators only)

## 7 STUDY DESIGN

This is a prospective, single-center, open-label, single-arm, observational study assessing participant experience with swallowing the Mock-RP.

### 7.1 Participant Selection

Participants  $\geq 21$  years old who are currently taking injections to treat chronic disorders (e.g., diabetes (I or II), rheumatoid arthritis, ulcerative colitis, Crohn's disease, ankylosing spondylolisthesis, psoriasis, growth hormone deficiency, hemophilia A) will be enrolled.

## 7.2 Study Inclusion and Exclusion Criteria

Upon confirmation that a consented participant meets all inclusion criteria and none of the exclusion criteria, the participant is considered eligible for randomization, and the study procedure can be scheduled.

### 7.2.1 Inclusion Criteria

Individuals eligible to participate in this study must meet all the following criteria:

1. Participant age is 21 – 75 years
2. Participant understands the nature of the study, is willing to comply with protocol defined evaluations, and provide written informed consent
3. Participant currently taking injections to treat a chronic disorder
4. Non-pregnant, non-lactating female

NOTE: Females who are of childbearing potential must have had a negative pregnancy test on day of screening

### 7.2.2 Exclusion Criteria

Individuals eligible to participate in this study must not meet any of the following criteria:

1. Active case of COVID-19
2. History of Dysphagia
3. History of dementia (e.g., Alzheimer's, vascular dementia, dementia with Lewy bodies, etc.)
4. Participant self-reports issues with swallowing pills.
5. History of drug or alcohol abuse or any other factor that, in the Investigator's opinion, may interfere with the participant's ability to cooperate and comply with the study procedures
6. History of allergic reaction to a component of the Mock-RP
7. History which, in the investigator's judgement, makes the participant ineligible or exposes the participant to unacceptable risks

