#### Additional CRF Edits:

- Screening CRF: Added new exclusion criteria for allergies to mock-RaniPill components.
- Moved Pill Swallow Assessment up the form.
- Post-Swallow Questionnaire: changed VAS score from 0-10 to 0-4.
- SAE Form: added "Final Outcome" field.

Associated Files 10 Reference File(s) + 0 Implementation File(s)

Routings None specified

Approval Deadline None specified

Effectivity 2021/04/28

Expiration Date N/A (This is a permanent Change.)

Lifecycle Status... Completed

...As Of 2021/04/28 03:38:17 PM

Creator [name]

Created On 2021/04/23 06:53:40 AM

Submitter [name]

Submitted On 2021/04/23 11:30:50 AM

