#### 7.5 Participant Accountability

Following completion of screening, participants will be assigned to their age group and have one study visit to swallow the Mock-RP and complete questionnaires ([Figure 2](#)).

[figure not shown]

Figure 2: Participant Accountability Overview

Screening and visit requirements are outlined in Table 1.

Table 1: Screening and Visit Requirements

	Swallow Visit
Inclusion/Exclusion criteria review	✓
Informed Consent	✓
Medical Hx/Demographics	✓
Weight/Height/Temperature	✓
Concomitant Medications	✓
Urine Pregnancy Test	✓ ^
Dispense Mock-RP	✓
Questionnaires	✓
Dispense Calcium Pill, if necessary	✓ *
Adverse Event(s)	✓

^ Pregnancy test completed on day of screening.

\* Dispense ONLY if participant is unable to swallow the Mock-RP

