#### 7.7.4 Calcium Pill Swallowing, if necessary

Participants unable to swallow the Mock-RP on the post-swallow questionnaire (responded “No” to “Did you manage to swallow the pill?”) will be asked to attempt to swallow a Calcium dietary supplement (Rapid Release Calcium in Liquid Softgel – contains 600 mg calcium as calcium carbonate per softgel and 500IU Vitamin D as D3 Cholecalciferol per softgel). The participant should rinse their mouth with water before attempting to swallow the calcium pill then swallow the pill the way they always swallow pills, without chewing.

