## 10.7 Anticipated Adverse Events

Known potential risks of swallowing the Mock-RP include:

- Oropharyngeal symptoms (coughing, gagging, etc.)

- Airway obstruction due to accidental aspiration
- Dysphagia
- Nausea/vomiting
- Dyspepsia

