### 10.8 Adverse Event Reporting

All adverse events occurring from the start of any study specific screening procedures must be recorded in the eCRF. Adverse events identified and reported in this study will be classified in accordance with the adverse event diagnosis and reported to the IRB per local requirements.

AEs must be recorded on the eCRF and be described by (a) duration (start and resolution dates); (b) signs and symptoms; (c) final event diagnosis; (d) event severity; (e) Investigator's clinical opinion on the relationship to the study CTM; (f) action taken to resolve the event; (g) outcome of the event; and (h) whether or not such event is considered to have been serious and/or unanticipated.

Adverse events should be reported according to their underlying cause, if known. Multiple symptoms related to a single diagnosis should not be reported as separate AEs. Only concomitant AEs that are unrelated to each other (in the clinician's judgment) should be reported as separate events.

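### The calcium softgel given after a failed Mock-RP attempt falls outside the product-specific allergy, risk and relatedness provisions, so sensitivity to it is not specifically screened and its adverse events cannot be reliably separated

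*Combined protocol and SAP*

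**What the plan says.** Section 7.7.4 states that participants who answer No to having swallowed the Mock-RP "will be asked to attempt to swallow a Calcium dietary supplement". It gives the softgel's calcium carbonate and vitamin D3 content. Table 1 in section 7.5 lists the softgel within the single swallow visit, with the footnote "Dispense ONLY if participant is unable to swallow the Mock-RP". The visit is expected to last about one hour.

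The product-specific safety provisions are worded as follows:

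- Section 7.2.2, exclusion 6: "History of allergic reaction to a component of the Mock-RP". The change-order record describes the matching form edit: "Screening CRF: Added new exclusion criteria for allergies to mock-RaniPill components".
- Section 10.7 opens its list with "Known potential risks of swallowing the Mock-RP include".
- Section 11.1 attributes risk to the Mock-RP, by reference to 10.7, and to taking part in a study.
- Section 10.4 grades causality against the study CTM, and 10.8 requires the investigator's "clinical opinion on the relationship to the study CTM". The synopsis lists the Mock-RP as the CTM, and section 3.3 describes it as the investigational CTM. The softgel is not described as CTM anywhere.

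One general provision reaches further. Exclusion 7 is not tied to a product: "History which, in the investigator's judgement, makes the participant ineligible or exposes the participant to unacceptable risks".

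**The concern.** The softgel is not something a participant happens to be taking. The protocol itself hands it out, and only to people who have just failed to swallow a large capsule. Two things follow from leaving it out of the product-specific provisions.

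First, a participant can be given the softgel without having been asked about sensitivity to its ingredients, although the corresponding question is asked for the Mock-RP.

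Second, gagging, nausea or a similar complaint in this group may follow two swallowing attempts made within about an hour. If the record cannot place the onset between them, or link the event to one product, the adverse event listing is hard to interpret for the participants in whom it matters most.

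No swallowability estimate is at stake. The issue is the completeness of screening and the readability of the safety data.

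**Working it through.** The plan states no figure on this point, so there is nothing to reproduce. The check sets the provisions side by side and then sizes the group.

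**Step 1: coverage of each product**

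| Provision | Mock-RP | Softgel |
|---|---|---|
| Specific allergy exclusion (7.2.2 no. 6) | yes | no |
| Exclusion for unacceptable risk (7.2.2 no. 7) | yes | yes, at the investigator's discretion |
| Medical history and medication record (7.6.2, 7.6.3) | yes, general | yes, general |
| Anticipated events (10.7) | yes | no |
| Risk section (11.1) | yes | no |
| Capture of adverse events (10.1, 10.8) | yes | yes, regardless of relation |
| Relatedness grade (10.4, 10.8) | yes | none of its own; may be cited as an alternative cause |

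The specific provisions cover one product and the general ones cover both.

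**Step 2: can the required fields separate the products?** Section 7.7.4 fixes the order: Mock-RP attempt, post-swallow questionnaire with the answer No, then softgel. For timing, 10.8 requires start and resolution dates. Both attempts fall on the same date, so a start date cannot place onset before or after the softgel. For cause, 10.8 requires relatedness to the CTM only. Under 10.4, onset within a reasonable time of the CTM is evidence for a possible relation, and an event shortly after the softgel is also shortly after the Mock-RP attempt. A clinician who knows that the softgel was the cause can say so, but an ambiguous event cannot be resolved from the required fields.

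**Step 3: how many participants?** Inputs: three age groups of 30 to 50 (section 5), so n = 3 × 30 = 90 to 3 × 50 = 150 attempting the Mock-RP. The documents give no expected failure rate f; 2% to 10% is assumed. If everyone who fails goes on to try the softgel:

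- Expected number = n × f
- Chance of at least one = 1 − (1 − f)^n, treating participants as independent

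| f (assumed) | Expected, n = 90 | Expected, n = 150 | P(at least one), n = 90 | P(at least one), n = 150 |
|---|---|---|---|---|
| 2% | 1.8 | 3.0 | 0.838 | 0.952 |
| 5% | 4.5 | 7.5 | 0.990 | above 0.99 |
| 10% | 9.0 | 15.0 | above 0.99 | above 0.99 |

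Some use of the softgel is likely, in a group of roughly 2 to 15 people.

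**The case against.** The strongest reply is that the general provisions are enough. Exclusion 7 is not limited to the Mock-RP. Section 7.6.2 takes a medical history, and 7.6.3 records non-prescription as well as prescription products. Section 10.1 counts events whether or not they relate to the CTM. Section 10.8 asks for reporting by underlying cause where it is known. Section 10.4 accepts other pharmaceuticals or chemicals as an explanation, and requires a documented alternate cause before an event is graded unrelated. The group is also likely to be small: people with dysphagia or self-reported pill problems are excluded, and section 2.3 reports no swallowing issues in the previous studies, although those were in young healthy volunteers.

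Most of this stands, and it rules out three stronger readings that a reader might infer.

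- **Softgel hazards are unscreened.** They are not: the general exclusion and the history apply. What is missing is a specific prompt. The investigator can act on a sensitivity that comes to light, but nothing in the plan requires the question.
- **Softgel events will be misattributed, or must be graded as not related.** The text forces neither. A known softgel cause has a place in the record, and grading such an event as unrelated to the Mock-RP would be correct. The gap concerns events whose cause is unclear.
- **The Mock-RP adverse event rate will be distorted.** The endpoint in section 4.1 counts all adverse events by type and frequency. The plan defines no rate attributable to the Mock-RP, and any size put on such a distortion would rest on invented event counts.

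Two limits also apply. The case report forms are not in the documents, so the adverse event form may already record onset time or a second product. The consent pages were removed, so whether consent covers the softgel cannot be judged.

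**Conclusion.** The point holds as a gap in coverage. The softgel is dispensed under the protocol but is missing from the specific allergy exclusion, the anticipated risks, the risk section and the relatedness grading. Its screening rests on general provisions that do not prompt the question. The adverse event fields that section 10.8 requires cannot reliably separate two products taken on the same date within about an hour.

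The scale is small: about 2 to 15 of 90 to 150 participants at an assumed failure rate of 2% to 10%, with an 84% to 95% chance of at least one even at 2%. The attribution part also assumes that the adverse event form collects no more than 10.8 requires. This is an inexpensive improvement to make, and it does not put the study's main estimate in doubt.

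**What to change.** Reconcile sections 7.2.2, 10.4, 10.7, 10.8 and 11.1 with 7.7.4 so that each covers every product the protocol dispenses. Specifically:

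1. Add a screening question on sensitivity to the softgel's ingredients. The consequence of a positive answer is for the sponsor and investigator to set; none is proposed here.
2. Unless the adverse event form already does so, record whether onset was before or after the softgel, and relatedness to each product separately. The post-swallow questionnaire, completed before the softgel is offered, gives a clear dividing point.
3. Flag post-softgel events in the adverse event listing. Separate tables are optional, given how few people are involved.

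The cost is one line on the screening form, two adverse event fields and matching protocol wording. The adverse event fields need completing only for the few participants who receive the softgel and have an event.

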## 7.3 Enrollment

Up to 200 men and women volunteers age  $\geq 21$  currently using injection therapy will be recruited from the general population and enrolled (consented) and up to 150 participants will attempt to swallow the Mock-RP after passing protocol required screening. A total of 30 to 50 participants will be included in each of the following age (years) groups: 21-50, 51-65, 66-75. Participants must meet all inclusion and none of the exclusion criteria prior to swallowing the Mock-RP.

## 7.4 Informed Consent Process

Informed Consent is a legally effective, documented confirmation of a participant's voluntary agreement to participate in a clinical investigation after the information has been given to the participant on all aspects of the clinical investigation that are relevant to the participant's decision to participate. The ICF will be approved by an IRB prior to the commencement of the clinical investigation at an investigative site. Any changes to the ICF must be approved by the IRB

reviewing the application before being used to consent a prospective study participant. It is recommended, but not required, that changes made to the ICF be submitted to Rani Therapeutics for review prior to being used to consent a prospective study participant. The current IRB approved version of the ICF must be used. Participants must provide informed consent prior to any study-related procedures.

The process of obtaining a participant's informed consent will:

- Ensure that the PI or his/her authorized designee conducts the informed consent process
- Include all aspects of the clinical investigation that are relevant to the participant's decision to participate throughout the clinical investigation
- Provide opportunity for participant to ask questions
- Avoid any coercion or undue improper influence on, or inducement of, the participant to participate
- Not waive or appear to waive participant's legal rights
- Use native language that is non-technical and understandable to the participant
- Provide ample time for the participant to read and understand the informed consent form and to consider participation in the clinical investigation
- Ensure participant, or an authorized designee responsible for conducting the informed consent process, dates and signs the ICF. The investigator and research staff cannot sign or date the ICF for the participant.
- The original signed and dated ICF and documentation of the consent process must be retained at the investigative site and available for monitoring and auditing.
- Show how informed consent is obtained and recorded in special circumstances (e.g., participant needing legally designated representatives, participant unable to read or write) where the participant is unable to provide it
- A copy of the signed and dated ICF (and data privacy language where required by law) must be provided to the participant (or person who signed the form in the case of a legally authorized representative).
- Data protection authorization/or other privacy language needs to be collected where required by law or local regulation.
- If using an electronic ICF, there needs to be a documented electronic signature process which is in compliance with applicable regulations (refer to 21 CFR part 11).
- It is recommended that the informed consent process is documented in the participant's medical records.

Any new information should be provided to the participant if it could affect the participant's willingness to participate.

